Objective(s):	For these reasons we developed this study with a short educational video concerning global management of local anaesthesia on outpatient hand surgery. The aim of this trial was to assess the impact of this educational video about perioperative patients' anxiety levels.
Outcome (if applicable, see Basisformular): Primary Outcome Secondary Outcome	The principal outcome was to see and analyse the difference in preoperative anxiety between the two groups measured on our adapted visual analogue scale (VAS-A). Secondary outcomes were to perceive any disparity in patient's satisfaction degree measured through final questionnaire, and any variance in vital parameters that are usually affected by anxiety (like arterial blood pressure [mmHg], respiratory rate [breath per minute] and heart rate [beat per minute]) in all patients. A subgroup analysis was then performed, but applied to specific subgroups, like anxious patients, higher anxiety score (3 or more) and patients at their first experience with surgery.
Study Design, see Basisformular:	This is a prospective, randomized, controlled clinical trial.
Inclusion/Exclusion Criteria, see Basisformular:	Inclusion criteria were patients older than 18 years, ASA I-III patients undergoing elective hand-surgery operation and patients anesthetized by IVRA. Exclusion criteria were patient refusal, on-going anxiolytic or anti-depressive therapy, diagnosis of anxiety or psychiatric disorders, general contraindications to IVRA, limited compliance or language barriers.
Measurements and Procedures:	Patients were admitted on the same day of surgery in the day-hospital clinic, 2-3 hours before the operation; all vital parameters (non-invasive arterial blood pressure, respiratory and heart rate) were measured and they were asked to indicate their initial level of anxiety using some validated instrument, like the VAS-scale (discussed right below). Patients were randomized with a free web tool (available at www.randomizer.org) in a consecutive order into two parallel groups; last Author was the responsible of this randomisation and he was not directly involved in patient treatment. Surgeon and investigators involved in subsequent data analysis were blinded to group assignment.

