Study Product/Intervention according to KlinV, if applicable:	One hour before surgery, patients assigned to the video-group (group I) visualised a Patient Education Video , a brief video (6 minutes). Patients in the film group watched the movie using a laptop computer equipped with headphones, and VAS score (Visual Analogue Scale) was repeated after the film. Video was recorded by the Anaesthesiology department team, in order to explain and show in a detailed way on a model, the sequence of events, which occurs between the arrival of patients in the operating room and the performance of intra-venous regional anaesthesia. The video began with an actress interpreting a patient scheduled for an elective outpatient hand surgery procedure acceding the day hospital clinic. It showed the interaction between the patient and the nurses who explain in details what is going to happen next and lead her through the preparation routine. The camera then followed the patient as she is accompanied to the induction room and the video showed all the details of the checks made as the patient accedes the operating room, the time-out and the preparation for the anaesthetic procedure, with the monitoring of the vital parameters. Then the intra-venous regional anaesthesia procedure was shown in details as an anaesthesiologist explains it step by step. The video concluded with the patient being brought to the operating room and staying awake and pain free as a simulated procedure begins.
Comparator(s) (if applicable):	Patients assigned to the control group (group II) did not see the video and underwent an otherwise identical preoperative preparation procedure.
Study Duration:	Around 8-9 months

Study Schedule:	From April to December 2013
Investigator(s):	
1. Dr. med. [name] Medico Aggiunto, Dip. Chirurgia della Mano ORBV, Bellinzona
 
2. Dr. med. [name] Medico Assistente, Serv. Anestesia ORBV, Bellinzona
 
3. Dr. med. [name] CapoClinica Medicina Intensiva, HUG, Geneva
 
4. Dr. med. [name] VicePrimario Chirurgia Toracica, ORBV Bellinzona
 
5. Dr. med. [name] VicePrimario Chirurgia Generale, ORBV Bellinzona
 
6. Dr. med. [name] VicePrimario Serv. Anestesia e Rianimazione ORBV, Bellinzona

Study Centre(s):	This is a single-centre study, to ORBV, Bellinzona

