Statistical Analysis incl. Power Analysis	A power analysis was conducted before starting recruitment. According to Ayrat et al, as well according to estimated clinically relevance of diminution for anxiety, assuming a reduction of at least 50% in preoperative anxiety level as clinically significant, 45 patients per group were necessary (allowing for drop-outs) to reach a 95% level of significance with a power of 90%. We conducted a statistical frequency analysis regarding common vitals parameters and anxiety level according to VAS-scale at arrival in the hospital, before to go to the pre-operative room and at arrival at the pre-operative room, performing a statistical frequency analysis comparing all these three steps and all subgroup according to secondary outcomes.
GCP Statement:	This study will be conducted in compliance with the protocol, the current version of the Declaration of Helsinki, the ICH-GCP or ISO EN 14155 (as far as applicable) as well as all national legal and regulatory requirements.

Recruitment Procedure (if applicable: Advice/Flyer have to be submitted ; if applicable, please indicate the Localisation / Medium (which Newspaper))

All patients underwent two surgical pre-operative visits, during which they received detailed information about surgical procedure and provided their informed consent.

Study Procedure/Flowchart with Timelines: Study specific Examinations have to be clearly identified

Patients were randomized with a free web tool (available at www.randomizer.org) in a consecutive order into two parallels groups; last Author was the responsible of this randomisation and he was not directly involved in patient treatment. Surgeon and investigators involved in subsequent data analysis were blinded to group assignment. One hour before surgery, patients assigned to the video-group (group I) visualised a *Patient Education Video*, a brief video (6 minutes) better described below. Patients assigned to the control group (group II) did not see the video and underwent an otherwise identical preoperative preparation procedure. Patients assigned to the two different groups were kept always separated while waiting for surgery.

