After the end of the video and at least 30 minutes before the transfer to the operating room (OR), investigators asked patient to indicate again its own anxiety level. Non-invasive arterial blood pressure, cardiac and respiratory frequency were recorded once again on arrival in the OR and monitored continuously throughout the anaesthetic and surgical procedure.

IVRA was performed by an anaesthesiologist and a nurse in the induction room outside the OR using a standardized procedure. Two intravenous lines were placed on each hand; after tourniquet inflation, a total volume of 40 ml of chloroprocaine 0.5% was injected intravenously in the operated limb. The patient was then transferred to the OR and 10 minutes after local anaesthetic injection, the surgeon tested loss of sensitivity with a pinprick test, after which surgery began.

As anxiety is a highly subjective psychiatric disorder, according to other investigational groups we felt that the best way to determine the state of anxiety is to let it evaluate directly by the patient. The VAS score (Visual Analogue Scale) is a valid instrument used for measuring anxiety. We chose an adapted VAS score (VAS-A), a semi-quantitative numerical scale (0 – 5 level) to measure patients' anxiety level, asking each patient to subjectively quantify its own anxiety, putting a mark on this visual scale, representing its actual anxiety degree.

At the end of the surgical procedure all patients were transferred directly to the day-hospital clinic. Between 1 - 3 hours after the operation all patients completed a satisfaction questionnaire with close evaluation from 0 to 10 regarding these topics: environment, equipment, organization, waiting time, pharmacy, nurses, professionalism, information, dedicated time. Moreover, video-group patients received a specific feedback questionnaire about the video, in which they were asked about personal satisfaction and video's education value (like informative and a valuable source of information for patients before local anaesthesia). Finally, we asked them if the educational movie made them more anxious or calmer.

Risks/ Inconveniences, which are Study specific:

No risk, because the intervention is a movie of 6 minutes.

Coverage of Damages: Insurance (yes/no)? Sum?

No

Storage of Data-and Samples for Future Research Aims: yes/no?,

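### The analysis compares vital signs and VAS-A across three steps, but the schedule gives each variable only two discrete readings, so the three-step comparison cannot be run as written

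*Combined protocol and SAP*

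**What the plan says.** The Statistical Analysis row describes a frequency analysis of vital signs and VAS anxiety at three times: "at arrival in the hospital, before to go to the pre-operative room and at arrival at the pre-operative room". It then states the comparison as "performing a statistical frequency analysis comparing all these three steps".

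The readings themselves are described elsewhere:

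- **Admission (Measurements and Procedures).** Patients arrive at the day hospital 2-3 hours ahead of surgery. For vital signs the row says of that visit: "all vital parameters (non-invasive arterial blood pressure, respiratory and heart rate) were measured". A first anxiety rating is described for the same visit: "they were asked to indicate their initial level of anxiety".
- **Second VAS-A.** The Study Product/Intervention row says, for the film group, that the "VAS score (Visual Analogue Scale) was repeated after the film". The Study Procedure/Flowchart section places this rating after the video ends and 30 minutes or more before the patient goes to the OR.
- **Second vital signs.** The Study Procedure/Flowchart section names blood pressure together with the other two signs and says: "cardiac and respiratory frequency were recorded once again on arrival in the OR and monitored continuously throughout the anaesthetic and surgical procedure".

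The Outcome row gives preoperative anxiety on VAS-A as primary, and as a secondary outcome "any variance in vital parameters that are usually affected by anxiety". Neither is tied to a reading time.

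**The concern.** An analysis across three steps needs each variable measured at each step. The schedule appears to describe two different pairs of times, one for vital signs and one for VAS-A, and the analysis row appears to merge them into a single three-step series that no variable has. An analyst following the text would find an empty cell in every series and would have to decide what the comparison means.

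Two things are at stake. The first is the comparison across steps, which the row states for all variables. The second is the vital-sign secondary outcome. Its wording fixes no time, and its one scheduled repeat is located by a room whose place in the sequence is unclear. If OR arrival follows the block, that reading reflects the procedure as well as anxiety.

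**Working it through.** No sample-size or power figure is involved, so the check sets the analysis steps against the scheduled readings.

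| Step in the Statistical Analysis row | Vital signs (discrete) | VAS-A |
|---|---|---|
| 1. Hospital arrival | Yes: Measurements and Procedures | Yes: Measurements and Procedures |
| 2. Before leaving for the pre-operative room | None scheduled | Yes: Study Procedure/Flowchart; Study Product/Intervention |
| 3. Arrival at the pre-operative room | Only if this room is the OR: Study Procedure/Flowchart | None scheduled |

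**Count.** VAS-A has 2 of 3 steps. Each vital sign has 2 of 3 if the pre-operative room is the OR, and 1 of 3 if it is not. No variable has 3 of 3 under either reading.

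**Step pairs.** Three steps give three pairs: 1-2, 1-3 and 2-3. VAS-A can fill 1-2 only. Each vital sign can fill 1-3 only, or none of the listed pairs if the rooms differ. No variable can fill 2-3.

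**Continuous monitoring.** It is described for the anaesthetic and surgical procedure, so it is not described as covering step 2. At most it might supply a step 3 value for vital signs. The documents do not say that any monitor value was stored or analysed.

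**Room names and order.** The plan uses pre-operative room, induction room and OR without linking them, and the text points both ways on the order of OR arrival and block.

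- *Arrival after the block.* The Study Procedure/Flowchart section puts the block in an induction room outside the OR and has the patient moved to the OR afterwards. The video description in the Study Product/Intervention row likewise ends with the move to the operating room.
- *Arrival before the block.* The Study Procedure/Flowchart section records vital signs on OR arrival and then monitors through the anaesthetic. The video description also speaks of events that run from arrival in the operating room up to the block.

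**What a post-block reading would do.** Suppose the procedure adds the same shift *c* to a vital sign in both arms, and let *v* and *k* be the mean changes from admission without that shift in the video and control arms.

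- Within-patient change across steps: *v + c* and *k + c*. The shift stays in.
- Between-arm difference: (*v + c*) - (*k + c*) = *v - k*. The shift cancels.

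So, under either order, a common shift does not distort the between-arm contrast. It matters only for the comparison across steps, and only if arrival follows the block.

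**The case against.** The strongest reply is that the three steps are a pooled list of all assessment times. If the pre-operative room is the OR, the list then matches the schedule exactly, and each variable can be compared from admission to its own repeat. That explains the list. It does not explain the stated comparison of all three steps, which no variable allows, and it needs an identity between rooms that the documents do not state.

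A second reply is that the analysis row is in the past tense and may itself report readings that the procedure section under-describes. This stands in part: the documents cannot exclude that such readings were taken. The remedy should therefore ask before anything is dropped.

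A reader might also infer three stronger points that the documents do not support:

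- **That the analyst has wide freedom to pick a reading after seeing the data.** Each variable has one scheduled discrete repeat, so little is left to choose for VAS-A. For vital signs, real choice arises only if monitor values were kept and used, which the documents do not say.
- **That the repeat vital signs are contaminated by the block.** This rests on an order that the text leaves open, and a common shift cancels between arms.
- **That a monitor value from before cannulation should replace the OR-arrival reading.** That would redefine the outcome after a trial scheduled for April to December 2013 and described in the past tense. It could mix reading times across patients, and it relies on data not known to exist.

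**Conclusion.** The point holds as an internal contradiction. As written, the three-step comparison cannot be run for any of the four variables, because each has at most two of the three steps by discrete recording. This is true even on the reading most favourable to the plan.

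The consequence is limited. The between-arm comparison at the repeat reading remains feasible for VAS-A and for vital signs. What is lost is the comparison across three steps, along with a clear definition of the vital-sign outcome. No bias or loss of power is claimed.

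The conclusion assumes that the procedure sections list all discrete readings. It also assumes that controls had the second VAS-A at a comparable time: the Study Product/Intervention row states the repeat only for the film group, and the Study Procedure/Flowchart section times it by the end of the video, with no matching clock time for controls.

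**What to change.** 1. Reconcile the Measurements and Procedures, Study Product/Intervention, Statistical Analysis and Study Procedure/Flowchart texts on room names, recording times (including the control group's second VAS-A) and the order of OR arrival and block. State for each variable whether any reading was taken at its missing step.
2. Unless such readings are confirmed, replace the three-step comparison with one between-arm comparison per variable at its scheduled repeat: VAS-A after the video and before transfer; vital signs on arrival in the OR. Use ANCOVA: repeat value = intercept + arm effect + slope x admission value + error, reporting the arm effect with its confidence interval. The admission values are already collected.
3. Report any monitor values descriptively.
4. If the OR-arrival reading turns out to follow the block, limit interpretation of vital signs to the between-arm contrast and say so.

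The cost is rewording and a little more analysis work, with no new measurement. The within-patient three-step comparison is given up, but the schedule does not support it.
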